4.4 Toxicity Management

All clinical and laboratory abnormalities will be followed closely until resolution. The urgency and frequency of repeat evaluations will depend on the clinical significance of the specific abnormality. Study clinicians will provide appropriate clinical management of adverse events according to their best medical judgment and local practice. As described in Section 6.1, the PSRT will closely monitor participant safety data on an ongoing routine basis throughout the study. The PSRT will also participate in the decision-making regarding study drug discontinuation and resumption.

4.4.1 Criteria for Adjusting or Discontinuing Study Drug

BUP/NX dosage may be adjusted routinely during the induction and stabilization phase of the study for participants in the substitution treatment arm. Following stabilization, participants who meet any of the following criteria may have study drug dosage adjusted or discontinued with appropriate dose tapering:

- Intoxication with any drug at the time of the dispensing visit
- In need of temporary use of a medication that may interfere with BUP/NX (see Section 4.5)
- Serious adverse event (SAE) not related to withdrawal that is potentially related to the study drug
- Pregnancy
- Enrollment in another study that, in the judgment of the investigator, will interfere with full participation in or interpretation of HPTN 058
- Evidence of hypersensitivity to BUP/NX
- Participant's request
- Investigator's decision
- Continued dosing or dosing at the current level is contraindicated for any reason, as judged by the study clinician and/or PSRT (e.g. elevated ALT)

Decisions regarding resumption of study drug following discontinuation will be made in consultation with the PSRT. If drug interruption occurs for two weeks or longer, induction may need to be repeated. Further details regarding discontinuing or adjusting study drug will be specified in the treatment manual.

Participants who discontinue the study treatment (drug and/or counseling components) will remain in the study and continue all follow-up assessments as originally scheduled.

Those participants that were permanently discontinued from the study treatment under protocol version 1.0 will be eligible to re-start study medication prior to the dose tapering period after consultation with the PSRT.

NOTE: HIV seroconversion is not a reason for discontinuation of study drug, although those who receive protease inhibitors may have their BUP/NX dose adjusted.

4.4.2 Considerations for Women who Become Pregnant during the Study

BUP/NX is a pregnancy Category C drug. High doses of buprenorphine can pass through breast milk. Therefore, women who are pregnant or lactating are excluded from enrollment. During the informed consent process, local site staff will discuss the available data on BUP/NX and pregnancy with female study volunteers. Given the limited data on the safety of BUP/NX use throughout pregnancy, women who become pregnant will be discontinued from BUP/NX, with gradual tapering, for the duration of their pregnancy. Pregnant women will also be counseled about the risks and benefits of drug treatment during pregnancy and will be provided with referrals for alternative treatment options including methadone and buprenorphine alone when available.

Urine pregnancy tests will be performed approximately every four weeks during BUP/NX treatment. Pregnant women will be maintained in follow-up to ascertain study endpoint information. Clinical status of infants born to women who become pregnant while taking BUP/NX will be obtained by interview of the woman after delivery; if a woman withdraws from the study prior to completion of her pregnancy, every effort will be made to obtain this information. Reporting of fetal losses will follow DAIDS adverse event (AE) reporting requirements. Resumption of BUP/NX in women who have pregnancy losses, either spontaneous or elective, will follow the same procedures as those outlined in Section 3.5.1.

4.5 Concomitant Medications

Participants in the substitution treatment arm will be advised to consult with the study clinician before taking any other medications. Participants receiving the following medications should be monitored closely and *may* require dose adjustment:

Precautionary Medications

- CYP 3A4 inhibitors (e.g., azole antifungals such as ketoconazole, macrolide antibiotics such as erythromycin, HIV protease inhibitors). Participants receiving CYP 3A4 inhibitors may need their dose of BUP/NX reduced.
- CYP3A4 inducers (e.g., phenobarbital, carbamazepine, phenytoin, rifampicin). The
 interaction of buprenorphine with CYP3A4 inducers has not been investigated; therefore
 it is recommended that patients receiving BUP/NX should be closely monitored if
 inducers of CYP3A4 are co-administered.
- Narcotic analgesics, general anesthetics, benzodiazepines, phenothiazines, other tranquilizers, sedative/hypnotics or other central nervous system (CNS) depressants

Use of the above mentioned medications by participants in the substitution arm should be avoided unless such medication is clinically indicated by his/her primary care provider and alternative medications are either not available or are suboptimal for the indication for which they would be prescribed. All concomitant medications taken by participants in both study arms from screening

through the first 52 weeks of study participation, including other medications used for drug treatment such as methadone, will be reported on applicable study case report forms. In addition to prescribed and over-the-counter medications, street drugs, vitamins, herbal remedies, and other traditional preparations will be recorded.

Participants in both arms of the study will be advised of the risk of death or severe respiratory depression if they intravenously misuse buprenorphine, or concomitantly self-administer benzodiazepines, other depressants, including alcohol, or other opiates. BUP/NX should not be administered to patients who have been shown to be hypersensitive to buprenorphine or naloxone. For more details about adverse reactions and warnings, please refer to the drug package insert.

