4.3.3 Treatment Dose and Administration

To aid clinicians in determining the appropriate dose during the first two-to-three days, the study will use the Clinical Opiate Withdrawal Scale (COWS), an instrument measuring validated items of physical signs or symptoms of withdrawal, such as gooseflesh, vomiting, and sweating, to objectively assess withdrawal in both treatment arms. The total score gives an index of the participant's withdrawal intensity and can be administered over time to track changes and adjust dosing. On day one, the clinician will wait until the participant shows at least mild opiate withdrawal by monitoring with the COWS. If the score indicates at least mild withdrawal (the higher the score the more severe the withdrawal), the clinician will give 4 mg for the first dose. COWS will be repeated in one hour; patients will receive further dosing as described below.

Detoxification Treatment Arm

Medical detoxification utilizing BUP/NX will be initiated in participants randomized to the detoxification arm on the same day that randomization occurs. Using the COWS as described above, dosing will begin with a titration over a period of 3 days under direct supervision in the study clinic. On the first day of treatment, patients will initially receive a 4 mg dose of BUP/NX (expressed as the amount of buprenorphine) to be taken sublingually. Most participants will begin with a total first day's dosage of 8 mg. Up to 16 mg may be given on Day 2 and 32 mg on Day 3 depending on individual response. 135

Beginning on Day 4, participants will have their dosage of BUP/NX decreased by approximately 2 mg/day at the clinician's discretion until a dosage of 0 mg is reached. Thus the maximum number of days required for medical detoxification will be 18, i.e., for a patient who received 32 mg on Day 3 there will be 15 additional days over which the BUP/NX dose will be reduced to 2 mg with 0 mg being achieved on Day 19. Individuals who are inducted/stabilized on a lower maximum dosage will be medically detoxified over a shorter time period. Participants will come to the clinic daily (except on days when clinic is closed in which case a take-home dose will be given) for direct observation of dosing. Concomitant medications (such as acetaminophen for pain or loperamide for diarrhea) may be utilized in consideration of the cautions described in Section 4.5 of this protocol.

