Detoxification may be repeated at the 26 week time point if the participant in this arm is injecting and meets the criteria for opiate dependence. The clinician will repeat the eligibility questionnaires and all laboratory tests. If determined to be eligible for second detoxification, i.e., meets DSM-IV definition of opiate addiction, positive urine test, currently injecting at least 12 times in last 28 days, and does not have any contraindications (e.g., elevated ALT), detoxification procedures will be repeated as described above.

Substitution Treatment Arm

Dosing will begin with a titration over a period of two to three days under supervision in the study clinic using the COWS as described above. On the first day of treatment, patients will initially receive a 4 mg dose of BUP/NX (expressed as the amount of buprenorphine) to be taken sublingually. Most participants will begin with a total first day's dosage of 8 mg. On Day 2, up to 16 mg may be given. Up to 32 mg may be given on Day 3 and thereafter until three-times-weekly dosing begins. The induction strategy is primarily dependent on three factors: 1) time since last opiate use; 2) type of opiate (e.g., long or short-acting) used; and 3) degree of physical dependence. Therefore, each dosing schedule will be tailored to the individual participant.

Individuals randomized to the substitution treatment arm will come to the study site daily for direct observation of dosing until they have stabilized (for up to three weeks). Participants may be given a double dose or a take-home dose for days that the site is not staffed for dosing. After induction and stabilization, participants will be asked to come to the site for dosing three-times-weekly. The target dosage schedule for individuals whose daily dose was 16 to 24 mg/day is expected to be 32/32/48 mg administered on a three-times-weekly schedule (e.g., M/W/F); this is also the maximum three-times-weekly dosage. On rare occasions, for individuals who require more than 24 mg/day (i.e., 26, 28, 30, or 32 mg/day), it is unlikely that the 32/32/48 mg dosage schedule will be adequate. For those individuals, as well as for others who received 24 mg or less per day but for

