whom the 32/32/48 mg three-times- weekly schedule is not adequate, dosing may be continued on a daily basis through Week 52 of the study, with take-home doses administered for those days on which in-clinic dosing is not possible (e.g., 32 mg on M/Tu/W/Th/F/Sat with a take-home 32 mg dose on Sun). Participants receiving daily doses may also be given alternative day take home doses, which would conform to the visit schedule of those participants on three-times weekly dosing, at the discretion of the local investigators.

When dosed on a daily basis, the maximum agonist effects of buprenorphine will likely occur in a dosage range between 16 to 24 mg/day for most individuals. While increased dosages may not produce corresponding increases in agonist effects, they may extend the duration of buprenorphine-induced blockade of concurrently administered opiates. In one study, individuals maintained on 8 mg/day of buprenorphine solution were shown to tolerate a 72-hour dose omission well. 136

Study participants in the substitution arm will undergo dose tapering for approximately six weeks at the end of the treatment phase (weeks 47-52). As with dose induction, the visit schedule and dosage during dose tapering will vary from participant to participant. Although data are lacking regarding the identification of an optimal dosage reduction regimen, it is generally believed that a gradual reduction of BUP/NX over a longer period of time (e.g., the six-week period of the present protocol) is likely more effective and better tolerated that more rapid dosage reduction over short (e.g., 3 days) to moderate (e.g., 10-14 days) periods of time. For example, an individual maintained on a three-times-weekly dosage of 24/24/36 mg given on M/W/F could have his/her dosage decreased over six weeks according to the schedule in the following table:

Week of Study	Day of Week	Dosage (mg) of BUP/NX (Expressed as Buprenorphine Component)
	_	_
	M	22
47	W	20
	F	30
	_	
	M	18
48	W	16
	F	24
	M	14
49	W	12
	F	18
	M	10
50	W	8
	F	12
	M	6
51	W	4
	F	6
	M	2
52	W	2
	F	0

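### Two concomitant-medication rules in Section 4.5 name only the substitution arm, although detoxification participants also take BUP/NX

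*Protocol*

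**What the plan says.** Section 4.5 contains two preventive rules, each limited to one arm:

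- Consult first: "Participants in the substitution treatment arm will be advised to consult with the study clinician before taking any other medications".
- Avoid interacting drugs: "Use of the above mentioned medications by participants in the substitution arm should be avoided unless such medication is clinically indicated" and the alternatives are unavailable or suboptimal. The listed classes are CYP3A4 inhibitors, CYP3A4 inducers, and narcotic analgesics, benzodiazepines and other CNS depressants.

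Other parts of the section reach further. The instruction to monitor closely and possibly adjust the dose names no arm. Concomitant medications are recorded in both arms through week 52. The overdose warning is explicit: "Participants in both arms of the study will be advised of the risk of death or severe respiratory depression" if they misuse buprenorphine intravenously or self-administer depressants or other opiates.

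Section 4.3.3 describes BUP/NX dosing in the detoxification arm: "Up to 16 mg may be given on Day 2 and 32 mg on Day 3 depending on individual response", followed by a taper of about 2 mg/day from Day 4, for at most 18 days. Dosing is observed daily in clinic, "except on days when clinic is closed in which case a take-home dose will be given". Also, "Detoxification may be repeated at the 26 week time point" for those who again meet the criteria. The same text says that concomitant medications "may be utilized in consideration of the cautions described in Section 4.5 of this protocol".

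**The concern.** The need for both rules comes from taking BUP/NX, not from the arm label. A detoxification participant in the middle of a course has the same drug on board, possibly at a dose in or above the range where Section 4.3.3 says "the maximum agonist effects of buprenorphine will likely occur in a dosage range between 16 to 24 mg/day for most individuals". Section 1.1.5 reports deaths when buprenorphine was combined with other drugs, particularly CNS depressants such as benzodiazepines.

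Because Section 4.5 says so when it means both arms, a site reading it literally will take the restriction in the two rules as deliberate. It would then have no instruction there to tell detoxification participants to ask before taking another medication. Nor would it have a rule against avoidable prescribing of the listed drugs during the course. What is at stake is a small gap in participant protection, not the validity of the trial's comparison.

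**Working it through.** The main check is a comparison of text, with a short dose calculation to size the exposure.

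**1. Who each part of Section 4.5 covers**

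| Element of Section 4.5 | Arm named |
|---|---|
| Consult the clinician before other medications | Substitution only |
| Avoid listed drugs unless indicated | Substitution only |
| Monitor closely, possible dose adjustment | None named |
| Record concomitant medications to week 52 | Both |
| Warning on IV misuse and self-administered depressants | Both |

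**2. Whether the detoxification arm is exposed to the interaction**

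Section 4.3.3 starts BUP/NX in this arm on the day of randomization. Appendix V describes this arm as free of potential drug interactions only after the detoxification phase, which implies a potential during it.

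**3. Whether the unrestricted parts replace the two rules**

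- The both-arms warning concerns what participants take on their own. It does not mention CYP3A4 inhibitors or inducers, and it does not govern prescribed analgesics or sedatives.
- Monitoring begins once a listed drug is being taken. Consult-first advice acts before that.
- Section 3.2 excludes dependence on alcohol or benzodiazepines, not non-dependent use.

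**4. Size of the exposure**

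Inputs are from Section 4.3.3. The assumption is 8 mg on Day 1, 16 mg on Day 2, the peak dose on Day 3, then a reduction of 2 mg each day from Day 4 until 0 mg.

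Course length = 3 + (peak − 2)/2 days.

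- Peak 32 mg: 3 + 30/2 = 18 days. This reproduces the protocol's 18-day maximum, with 2 mg on Day 18 and 0 mg on Day 19.
- Peak 24 mg: 3 + 22/2 = 14 days.
- Peak 16 mg: 3 + 14/2 = 10 days.

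Days at 16 mg or more = Day 2, plus the days from the peak down to 16 mg, that is 1 + [(peak − 16)/2 + 1].

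- Peak 32 mg: 1 + (8 + 1) = 10 days.
- Peak 24 mg: 1 + (4 + 1) = 6 days.
- Peak 16 mg: 1 + (0 + 1) = 2 days.

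Ceiling as a share of the 52-week treatment year (52 × 7 = 364 days):

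- One course: 18/364 = 4.9%.
- Two courses: 36/364 = 9.9%.

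The planned arm size is 750 (Section 7.1). The documents give no rate of interacting-drug use in these participants, so no expected number of events follows.

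**The case against.** The strongest reply is that the protocol already handles most of this. The detoxification text of Section 4.3.3 points to the Section 4.5 cautions, and the natural reading carries them into that arm. The monitoring text names no arm, and both arms are warned about benzodiazepines, alcohol and other depressants, which is the main hazard cited. Section 4.3 promises a manual on BUP/NX administration that will cover concomitant medications. Dosing is short and mostly observed daily, so clinicians have regular chances to ask. The consent forms and manuals were not available for this review and may contain the missing advice.

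The risk argument also has limits. Section 1.1.5 says the reported deaths typically involved crushed tablets injected intravenously. The 16 to 24 mg/day range describes agonist effect and is not an interaction threshold. Ten days at 16 mg or more requires a 32 mg peak, and Section 4.3.3, speaking of the substitution arm, calls daily needs above 24 mg rare. An arm-based rule is understandable when one arm is exposed for 52 weeks and the other for days.

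Much of this stands as a limit on the size of the problem. It does not remove the inconsistency. The cross-reference leads to two cautions that, by their own words, leave out the arm being referred. The remaining text covers self-administered depressants and monitoring after the fact, not asking first or avoidable prescribing. What the manuals or consent forms say cannot be assumed in either direction, so the finding is confined to the wording of Section 4.5.

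**Conclusion.** The point holds as a minor safety-wording inconsistency. Two rules in Section 4.5 are tied to the substitution arm, although detoxification participants take the same drug and Section 4.3.3 relies on Section 4.5 for them.

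The gap applies to up to 750 participants, only while they are dosing: at most 18 days for one course and 36 for two. Under the assumed schedule, 2 to 10 days per course are at 16 mg/day or more, depending on a peak of 16 to 32 mg; the upper end is likely to be uncommon. No harm rate can be derived, and there is no claimed effect on the primary endpoint, sample size, power or analysis. Confidence is high for the wording itself. The practical consequence depends on manuals and consent forms not seen here. It is an optional, cheap improvement.

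**What to change.** In both sentences of Section 4.5, replace the reference to substitution-arm participants with: *participants currently receiving BUP/NX, in either arm, including a first or second detoxification course*. Leave the rest of each sentence unchanged, and carry the same wording into the treatment manual. The rules then follow drug exposure and lapse when dosing ends, so they place no standing restriction on the detoxification arm for the rest of the year.

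The cost is an amendment to two sentences and the manual, plus slightly more advice to detoxification participants. Concomitant medications are already recorded in both arms through week 52, so no new data are collected. Acetaminophen and loperamide, which Section 4.3.3 gives as examples for symptom relief, are not in the listed classes and stay available.

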5.0 STUDY PROCEDURES

An overview of the study procedures schedule is presented in Appendix I A and B. Participants randomized to the detoxification arm will be expected to complete approximately 45 to 60 visits (depending on whether or not a second detoxification is required) throughout the first year in the trial, while those in the substitution treatment arm will complete approximately 155-160 visits. The greater number of visits in the substitution treatment arm is due to three times weekly BUP/NX dispensing visits. Detailed instructions to guide and standardize all study procedures across sites will be provided in the SSP manual.

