2.3.1 Safety and Feasibility Phase

The study will begin with a safety phase during which each site will enroll 50 participants over a period of approximately six months. The primary purpose of this initial phase is to collect detailed safety data that will be made available to the sponsor and the appropriate oversight and regulatory authorities in Thailand, China, and the US, as needed. In addition, the feasibility and acceptability data on the first 50 participants in the study at each site will allow the sites to carefully plan for and establish appropriate full study operations, including procedures for study drug administration and monitoring.

The safety and feasibility phase will follow the same design as the full study, including 1:1 randomization, study drug administration, and counseling, but it will include a more intensive evaluation schedule for the first four weeks of an individual's participation in the study. For this initial phase, potential volunteers will be asked to sign a separate informed consent form that explains the additional evaluation requirements during the first four weeks of the study.

Evaluation of the initial safety and feasibility phase data will occur in two stages. The first stage will be site-specific (with available data from the two China sites likely combined) to be conducted after the 50th participant enrolled at each site completes four weeks of follow-up. The second stage will include data from all 150 safety and feasibility phase participants, in addition to other safety data accumulated up to that point, across all sites once the last participant enrolled completes four weeks of follow-up. The Statistical and Data Management Center (SDMC) will prepare comprehensive data summaries for each of the site-specific evaluations and the blinded interim evaluation for review by the Protocol Safety Review Team (PSRT) and at least one representative of the HPTN Study Monitoring Committee (SMC). The reviews will focus on both clinical and laboratory safety data and trial feasibility indicators such as screening, accrual, retention, and adherence to and acceptability of the study drug and

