2.3.2 Assessments during the Safety and Feasibility Phase

Participants in the safety and feasibility phase will follow all procedures and undergo all assessments as specified for the full study in Section 5.0. In addition, after enrollment, the clinical and laboratory evaluations listed below will be conducted every week for the first four weeks for participants in both study arms. Evaluation of participants in the detoxification arm will allow for comparison with those in the substitution treatment arm and will minimize differences in contact and attention between the two groups.

The following assessments will be employed:

- Interim medical history
- Symptom-directed physical exam
- Hemotology (Complete Blood Count [CBC] and platelet count)
- Blood chemistry (creatinine)
- Liver function tests (ALT, bilirubin)
- Urine tests for drug use
- Assessment of social harms
- Acceptability assessment at week 4

Management, reporting and review of adverse events and social harms will follow the procedures specified for the full study in Section 6.0.

Each participant will complete an intervention acceptability assessment at the completion of the fourth week of the study. Study staff not involved in delivery of the counseling or drug intervention components will administer these assessments.

Adherence to the intervention components will be measured by participants' completion of the individual counseling sessions and drug dispensing visits as scheduled during the first four weeks of the study.

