5.4 Assessments during Safety Phase

As described in Section 2.3.2 and shown in Appendix I-B, the first 50 participants enrolled at each site will undergo the following examinations and laboratory tests each week during the first four weeks of study participation in addition to the other activities listed in Section 5.5:

- Interim medical history
- Symptom-directed physical exam
- Hematology (CBC and platelet count)

- Blood chemistry (creatinine)
- Liver function tests (ALT, bilirubin)
- Urine tests for drug use
- Assessment of social harms
- Acceptability assessment at week 4

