5.5 Assessments During Full Study

In addition to intervention and laboratory visits, participants will be asked to come to the clinic every six months for clinical assessments including HIV testing and urine testing for opiates and other drugs. The week 24 counseling visit and the Week 26 follow-up visit may be combined into one visit to reduce participant visit burden. There should be no duplication of any laboratory test or the collection of any study information if the visits are combined. Visits will also include a behavioral assessment of HIV-related drug and sexual risk. More detailed assessments will be performed for all participants during the treatment phase of the study. The procedures for each visit are described below. Follow-up visits can be combined with monthly counseling sessions and BUP/NX dispensing visits.

ALT and bilirubin testing also will be performed at weeks 12 and 40 for all participants (in addition to tests completed at regularly scheduled follow-up visits); this blood draw will occur at the same visit as the urine test and counseling visit. Whenever clinically indicated, hepatitis B or C testing may be done by the study clinician.

Locator information will also be assessed at four-week intervals. To the extent possible, site staff will work with the participant to determine the best day of the week and time for this visit to be conducted each week (e.g., every Monday at 9 am). The counseling schedule will coincide with a BUP/NX dispensing visit, if possible, to minimize participant burden. Counseling visits may also be combined with follow-up visits.

5.5.1 26 and **52** Week Visits

These visits will include:

- Locator information update
- Symptom-directed physical exam, interim medical history
- Hematology (CBC, platelet count)
- Blood chemistry (creatinine)
- Liver function tests (ALT, bilirubin)
- Hepatitis testing (Week 26)
- Administer HBV vaccine if appropriate
- Urine testing for opiates and other drugs
- Pregnancy urine test for women in substitution arm and women in the detoxification arm who are undergoing a second induction
- Risk assessment (sex and drug use)
- Rapid HIV testing with pre- and post-test counseling
- Social harms assessment
- Intervention acceptability assessment

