5.6 Interim Visits

All participant visits to the study clinic or other contacts will be recorded in the study records. Any adverse events reported at clinic visits, procedures or tests performed will be appropriately documented on applicable case report forms and in the source documentation, according to the procedures detailed in the SSP manual. Female participants will be encouraged to come to the clinic for testing if they think they may be pregnant at any point during the study.

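### Outside the first four weeks of the safety phase, medical history is scheduled only at weeks 26 and 52, and SAE capture in between relies on visits that are far more frequent in the substitution arm

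*Protocol*

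**What the plan says.** Section 5.0 gives the expected year-1 contact by arm: "approximately 45 to 60 visits" for detoxification and "approximately 155-160 visits" for substitution. It gives the reason as well: "The greater number of visits in the substitution treatment arm is due to three times weekly BUP/NX dispensing visits".

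For the full study, Section 5.5.1 lists "Symptom-directed physical exam, interim medical history" among the week 26 and week 52 procedures. Appendix I-A marks both items in those two columns only, for both arms. For other visits, Section 5.6 says: "Any adverse events reported at clinic visits, procedures or tests performed will be appropriately documented". The protocol schedules no event question at counseling or dispensing visits.

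The safety phase is the exception. Section 5.4 says "the first 50 participants enrolled at each site will undergo the following examinations and laboratory tests each week during the first four weeks", and the list includes an interim medical history. Section 2.3.1 puts this group at 150 people ("data from all 150 safety and feasibility phase participants"). Section 2.3.2 explains that assessing the detoxification arm in the same way "will minimize differences in contact and attention between the two groups".

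Under Section 6.2, SAEs and other events needing expedited reporting enter the database in both arms through week 52. Other adverse events stay in source records.

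**The concern.** The trial is open-label, and the two arms meet study staff at very different rates. When no question is scheduled, an event reaches the database only if the participant mentions it or staff happen to learn of it. More visits give more chances for that.

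The staff differ too. Section 4.3 gives the clinicians who handle dosing the task of managing side effects. After at most 18 days of dosing, a detoxification participant's routine contact is with counselors, weekly to week 12 and then about every four weeks.

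At stake is the comparability and timeliness of non-fatal SAEs such as hospital admission or overdose. Section 6.2 starts the expedited-reporting clock at site awareness, so an event nobody asks about can start that clock late. The protocol treats unequal contact as worth controlling, but only for 150 of 1500 participants and only for four weeks.

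**Working it through.** **Inputs.** Visit counts: Section 5.0. Dosing schedule: Section 4.3.3. Counseling schedule: Sections 4.2 and 4.2.2. History schedule: Section 5.5.1 and Appendix I-A. Safety-phase size: Section 2.3.1. Total enrollment: Section 3.4.

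**1. Reproducing the plan's visit counts.**
- Substitution, three visits a week: 52 × 3 = 156. With 7 days of daily dosing: 7 + 51 × 3 = 160. With the full 21 days: 21 + 49 × 3 = 168.
- Detoxification: 18 dosing days + 12 weekly sessions + 10 four-weekly sessions (weeks 16 to 52) + week 26 + 2 screening visits = 43. A second 18-day course gives 43 + 18 = 61.

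These agree with the stated 155-160 and come within 2 visits of 45 and 60.

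**2. Ratio over year 1.** 155/60 = 2.6 at the lowest and 160/45 = 3.6 at the highest. At the midpoints, 157.5/52.5 = 3.0.

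**3. Ratio after week 12.** Substitution: 40 weeks × 3 = 120 dispensing visits. Detoxification: 10 four-weekly sessions + week 26 = 11. Ratio: 120/11 = 10.9. This assumes full attendance and no second detoxification. A full second course would make it 120/(11 + 18) = 4.1.

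**4. Time without a scheduled history.**
- From the end of an 18-day detoxification to week 26: 26 − 18/7 = 23.4 weeks.
- From week 26 to week 52: 26 weeks.
- The longest gap between scheduled contacts of any kind in the detoxification arm is 4 weeks. Section 5.5 allows the week 24 and week 26 visits to be combined. If that is done at week 26, one gap becomes 26 − 20 = 6 weeks.

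**5. Reach of the safety-phase exception.** 150/1500 = 10% of participants, for weeks 1-4.

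**6. Illustration of possible bias.** The protocol gives no capture rates, so these are assumptions. With equal true SAE rates, the apparent rate ratio (substitution to detoxification) is the ratio of the capture proportions.

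| Assumed capture, substitution | Assumed capture, detoxification | Apparent ratio |
|---|---|---|
| 95% | 90% | 1.06 |
| 95% | 80% | 1.19 |
| 95% | 70% | 1.36 |
| 95% | 50% | 1.9 |

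The range runs from negligible to large, and nothing in the protocol narrows it.

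**7. After the change.** Enquiries at weeks 4, 8 and 12 (3), weeks 16 to 52 every four weeks (10) and week 26 (1) give 14 per arm instead of 2. The longest gap falls from 26 to 4 weeks. If weeks 24 and 26 are combined, there are 13 enquiries, with one 6-week gap if the visit is held at week 26.

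**The case against.** The strongest reply is that the Study Specific Procedures (SSP) manual is not at hand. Sections 5.0, 5.6 and 10.2 leave detailed procedures, including adverse event assessment, to it, and it may already require an event question at every visit. That stands as a limit on the point. But the protocol's own schedule goes down to four-weekly urine tests and locator updates, and no event question appears there.

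Second, much capture is the same in both arms. ALT and bilirubin are tested at weeks 12 and 40 in everyone (Section 5.5). Concomitant medications are recorded through week 52 (Section 4.5). A missed dosing or counseling visit prompts a contact attempt within a day (Section 4.1). Deaths can be found from outside sources (Section 7.2). This stands, and it confines the point to non-fatal events. Dispensing visits carry no scheduled event question either, so unequal questioning is an inference from contact and staff roles.

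Three stronger readings are tempting, and the documents do not support them.
- A reader might infer that events after detoxification go unseen for months. They need not: participants are seen about every four weeks, may report events then, and the next history covers the whole interval. The risk is a late or forgotten report.
- A reader might infer that relapse and overdose are risks of the detoxification arm alone. Appendix V lists rapid return to drug use for both arms, and the warning about depressants in Section 4.5 goes to both.
- A reader might infer that the Protocol Safety Review Team compares SAEs by arm. No such comparison is stated. Section 2.3.1 gives that team a blinded interim evaluation and refers concerns to the DSMB for unblinded review. No primary or secondary endpoint is an SAE comparison, and Section 2.3 sets the adverse event data against US and European experience.

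**Conclusion.** The point holds as a weakness in the visit schedule. It is neither a contradiction nor an error in a stated figure. Followed as written, the schedule gives participants outside the safety phase two planned medical histories in year 1. In between, non-fatal SAE capture relies on contact that is about 3 times as frequent in the substitution arm over the year and about 11 times after week 12. The second figure assumes full attendance and no second detoxification.

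An SAE in the detoxification arm can go 23-26 weeks without a scheduled question, so it may be reported late or forgotten. Any resulting bias would tend to make substitution look less safe, but its size is unknown and no single rate ratio should be quoted for it. The primary endpoint is not touched. The conclusion assumes that the SSP manual adds no common event question. The change is worth making because it is cheap.

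**What to change.** In Appendix I-A and Sections 5.3 and 5.5, add one short event question set, worded identically in both arms: hospital admission, overdose, and serious illness or injury since last asked. Ask it at the existing four-weekly visits through week 52 and at week 26. If the SSP manual already contains such questions, cite them in the schedule and confirm that they apply equally to both arms.

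Count every SAE wherever it was first reported. Events first reported at dispensing visits should not be excluded or shown apart in the DSMB's by-arm summaries. Separating them would take substitution-arm events out of the comparison because they were reported sooner, and could reverse the bias.

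The cost is a few extra minutes at each four-weekly visit and somewhat more SAE forms. No new visits or staff are needed.
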